Project Title:

LIDOCAINE IN THE TREATMENT OF POST-OPERATIVE PAIN
MANAGEMENT FROM A DONOR SITE AFTER SPLIT THICKNES SKIN GRAFT
HARVESTING FOLLOWING BURN INJURY OR WOUND TREATMENTS

NCT #:

NCT02229578

Document date:

December 08, 2016

Protocol

1. Project Title:

LIDOCAINE IN THE TREATMENT OF POST-OPERATIVE PAIN MANAGEMENT FROM A DONOR SITE AFTER SPLIT THICKNESS SKIN GRAFT HARVESTING FOLLOWING BURN INJURY OR WOUND TREATMENTS

2. Investigator(s): **[name]**

[name]

[name]

[name], ARNP

[name]

3. Abstract:

Burn pain is known to be one the most severe forms of acute pain often requiring large amounts of narcotics in addition to other adjuvants. Wounds can also cause a great deal of pain in this population. Topical lidocaine is effective for controlling pain in various settings including dressing changes of burns. The aim of this study is to demonstrate the effectiveness of topical lidocaine in decreasing pain scores and narcotic requirements when applied to donor graft sites while at the same time not interfering with the standard of care TheraBond dressing. During this study we will be monitoring for evidence of delayed wound healing, and surgical site infection.

4. Background:

Pain from burns is a severe form of acute pain that requires aggressive use of opioids.¹ Even with the implementation of multiple modalities for analgesia, pain from skin debridements and grafting procedures remains a challenge to control.^{2,3} Local anesthetics have been used for pain relief in burn patients previously as a topical gel or IV infusion and have been found to significantly reduce medication consumption, without apparent adverse effects on wound healing.^{2,4,5} Lidocaine actually has potent anti-inflammatory effects which could be advantageous on wounds.¹ In addition, topical application of lidocaine to wounds result in different degrees of systemic absorption. High concentrations of lidocaine have potential for central nervous system (seizures ($>5\text{mg/L}$)) and cardiovascular toxicity (arrhythmias ($>9\text{mg/L}$)).⁴ Plasma concentration of lidocaine depend upon drug dose, rate of absorption, patient weight, physical status and thickness of skin harvested.⁶ A prior study where up to 6.7mg/kg of 2% lidocaine with epinephrine was sprayed on donor

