graft sites found that systemic lidocaine levels were far below toxic levels at their peak (average level of 1.4, with maximum level at 2.2). In this study the levels peaked between 30 and 60 minutes and systemic levels of lidocaine were detectable 6 hours following application of the solution.² Studies have demonstrated the beneficial effects of systemic lidocaine administered via IV infusions in reducing perioperative pain scores.^{7, 8} Topical lidocaine is effective as a topical anesthetic in multiple clinical trials however only two studies to date has shown that topical lidocaine applied to skin-harvest sites produces an analgesic effect, reduces narcotic requirements while not affecting wound healing or causing toxic blood concentrations. In both these studies systemic intravenous lidocaine levels were monitored and were found to be significantly below toxic limits.^{2,9} The use of topical lidocaine on donor sites is still not widely used, partly for fear the lidocaine will interfere with wound healing and/or dressing adherence. No study to date has demonstrated lidocaine solution to be effective on burn sites when used in conjunction with TheraBond silver foam dressing. TheraBond is an absorbent, atraumatic dressing coated with ionic silver that is routinely used on donor sites at our institution. This study will also offer additional supporting evidence that topical lidocaine is effective in post-operative pain management of donor skin sites and should be more widely utilized. In addition, this study will serve as a stepping stone for analyzing different local anesthetic solutions in the future and the potential for reapplication to surgical sites.

5. Specific Aims:

The purpose of this study is to offer the medical community data on a simple and relatively cheap adjuvant that can be utilized to help reduce the amount of post-operative pain and narcotic requirement in burn and wound patients requiring skin grafts.

6. Research Plan:

Study Design

- a) Randomized Controlled Double-Blind Study
- b) Burn and wound patients undergoing general anesthesia for split thickness skin graft with a 1-15% TBSA donor site who will be treated at UF Health Shands Hospital

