- c) Consent will be obtained from non-intubated patients willing to participate in the study that are admitted to the Burn Service for treatment of their burn or wound. All patients will undergo general anesthesia. Standard induction will be performed with Fentanyl and Propofol. Maintenance will primarily be with the volatile agent sevoflurane. Acetaminophen 1g IV and Ketorolac 30mg IV will be administered for baseline pain control intraoperative within the last 30 minutes prior to extubation. Fentanyl, Hydromorphone or Morphine will be

titrated in at end of the case as part of standard management. Hydromorphone, as needed (PRN), orders will be written for pain control in the recovery room as well as one time dose of Oxycodone 5-15mg PO. If patient requires more than 2mg of Hydromorphone then subsequent pain will be treated with Ketamine IV (10mg every 15 minutes up to 50mg total) and 1-2mg of IV midazolam. If pain is still not adequately controlled patient will be treated with an additional 2mg of Hydromorphone IV and Hydromorphone PCA will be initiated. Once discharged from the PACU to the surgical floor the patient will have PRN Oxycodone PO every 4 hours and/or Hydromorphone PO every 4 hours in addition to PRN Hydromorphone 0.2-0.5mg available. If pain control is still not adequate patient will be started on Hydromorphone PCA. The amount of hydromorphone required in PACU and in the first 24 hours following surgery will be compared between the two groups as well as self-reported donor site and overall pain according to the Verbal Numerical Rating Scale (VNRS) obtained from the patient by Research staff and by the hospital staff per standard of care.

- d) Lidocaine 2% with Epinephrine 10 μ g/mL will be placed on the donor site immediately following harvesting until hemostasis has been obtained per the surgeon. The total of up to 7mg/kg, as recommended by leading anesthesia textbooks, of lidocaine solution will also be sprayed onto the patient's donor site based on patient's ideal weight (BMI 25 or actual patient's weight if BMI <25).¹⁰
- e) 50 patients split into two (study & control) groups.

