 - a. Group A patients will have sterile 2% lidocaine with Epinephrine 10 μ g/mL (Solution A1) soaked in surgical grade cotton applied to the donor site immediately after donor harvest until hemostasis is obtained according to the surgeon. If additional hemostasis is deemed necessary by the surgeon following use of 20cc (1 vial) of this Solution A1 then additional Epinephrine 10 μ g/mL will be used as per standard burn protocol. Following hemostasis, patients will have a sterile, nonpyrogenic solution of lidocaine 2% in isotonic saline (Solution A2) sprayed on the donor site of the grafted skin prior to emergence from general anesthesia. A maximum of 7mg/kg of lidocaine solution will be available for spraying. The site will then be covered with TheraBond dressing as per standard burn care used at our institution.
 - b. Group B (control group) patients will have sterile Epinephrine 10 μ g/mL solution (Solution B1) soaked in surgical grade cotton applied to the donor site immediately after donor harvest. A 20cc aliquot will be prepared in such a way as to be indistinguishable from Solution A1 by the OR team. If additional hemostasis is deemed necessary by the surgeon following use of 20cc (1 vial) of this Solution B1 then additional Epinephrine 10 μ g/mL will be used as per standard burn protocol. Following hemostasis, patients will have a control (placebo) sterile, nonpyrogenic solution of isotonic saline (Solution B2) sprayed over the donor site. The site will then be covered with TheraBond dressing as per standard burn care used at our institution.

- f) Assessment of the donor sites using the VNRS pain scores will be compared between groups in addition to the amount of narcotic pain medication required by these two groups. The amount of narcotic utilized will be analyzed per ideal body weight, per actual body weight in addition to donor site area.
- g) Lidocaine levels will be drawn at sixty minutes and six hours from application of study solution. These levels will be analyzed on a per patient and per graft size area basis to trend for systemic levels.
- h) Any adverse event occurring with the patient will be analyzed on a case-by-case basis. Wound infection rates of the donor sites at post op day 14-21 +/- 5 days will be compared between the two groups. Any adverse event deemed serious by the Principal Investigator will be submitted to the Institutional Review Board per institution policy.

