- b. Randomization procedures: Numerical randomization will be created using a computer generated numbers. Randomization envelopes will be created by research staff and maintained by the Investigational Drug Pharmacy. The Burn Study Team will alert the Investigational Drug Pharmacy to randomize each patient. The Investigational Drug Pharmacy will dispense the appropriate blinded solution for treatment. The Investigational Drug Pharmacy will dispense Lidocaine with Epinephrine or Epinephrine alone in blinded fashion for the donor site soaks. A 20cc bottle of Lidocaine with Epinephrine or Epinephrine alone will be emptied into a sterile unlabeled container prior to application of sprayed study treatment. The surgeon and OR team will remain blinded for this portion of the study. If additional hemostasis is required beyond the first study soak treatment; then the standard of care epinephrine soak will be utilized. The Investigational Drug Pharmacy will also dispense the randomized spray study treatment in an assembled applicator (LMA MADgic™) purchased for this project only. No unblinding identifiers will be on either applicators. The investigator will be blinded to all groups. Study Intervention:
 - i. Group A (Lidocaine Treatment Group): Graft site hemostasis will be obtained with 2% lidocaine and epinephrine 10 μ g/mL solution in normal saline soaked in surgical grade cotton gauze and placed over donor site for time determined by surgeon. Following hemostasis, 7mg/kg of 2% Lidocaine solution will then be sprayed on patient's donor site while under general anesthesia by burn surgeon in a sterile fashion. Upon emergence and transfer to PACU patient will be asked to rate his/her pain according to the VNRS for both donor site and overall pain. The amount of narcotics required in PACU and first 24 hours on floor will be documented. Rate of increase of narcotic requirement within the first 24 hours will also be analyzed. VNRS scores will be obtained immediately post operatively on arrival to PACU and in 24 hours.

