 - ii. Group B(Placebo Group): Graft site hemostasis will be obtained with a epinephrine 10 μ g/mL solution in normal saline soaked in surgical grade cotton gauze and placed over donor site for time determined by surgeon. Following hemostasis a control solution will be sprayed on patient's donor site while under general anesthesia by burn surgeon in a sterile fashion. Upon emergence and transfer to PACU patient will be asked to rate his/her pain according to the VNRS for both donor site and overall pain. The amount of narcotics required in PACU and first 24 hours on floor will be documented. Rate of increase of narcotic requirement within the first 24 hours will also be

analyzed. VNRS scores will be obtained immediately post operatively on arrival to PACU, 6 hours post treatment during blood draw and in 24 hours for both donor site and overall pain.

Study Table of Events

Study Assessments	Baseline	Surgical Procedure	0-24 hours post op	24-48 hours post op	Follow up (14-21 days)*
Informed Consent	X				
Inclusion/Exclusion	X				
Demographic Data	X				
Medical History	X				
Physical Exam	X				
Randomization		X			
Treatment		X			
OR Data Collection		X			
VNRS Pain Assessment			X**	X**	
Self-Reported Pain Assessment			X	X	
Wound Healing Assessment					X
Photographs		X			X

Narcotic Medication Data Collection		X	X	X	
Adverse/SAE Assessment	X	X	X	X	X
Lidocaine Level			X***		

* (+/- 5 days)

**Performed at 30 minutes after extubation, 2 hours, 6 hours and 24 hours post-op for both donor site and overall pain

***Performed at 60(+/-30 minutes) minutes and 6 hours (+/-60 minutes) post op

Safety Monitoring Plan

- a. The likelihood of adverse events in this study is very small. Lidocaine spray doses will be calculated (7mg/kg based on ideal body weight) to ensure patient is receiving safe doses. A safety analysis performed on our first 15 patients proved safety. All lidocaine levels obtained demonstrated levels significantly lower than potentially toxic dosing. We believe there could be improved pain control if more appropriate (higher) lidocaine doses are utilized. The method suggested for hemostasis with lidocaine and epinephrine is standard of care at some institutions including our own. It is regularly used by the ENT service. In addition, one of the surgeons in our study has used this method in the past.
- b. Patients will be monitored with pulse oximetry overnight per standard of care.

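### The dose calculation offered as the safety assurance covers only the lidocaine spray, not the up to 400 mg allowed in the soak, and the lidocaine draws run on two different clocks

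*Combined protocol and SAP*

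**What the plan says.** **Spray.** Study Design (d) says "The total of up to 7mg/kg, as recommended by leading anesthesia textbooks, of lidocaine solution will also be sprayed onto the patient's donor site", with the dosing weight "based on patient's ideal weight (BMI 25 or actual patient's weight if BMI <25". Study Design (e), Group A, says "A maximum of 7mg/kg of lidocaine solution will be available for spraying". Study Intervention (i) gives an amount rather than a ceiling: "7mg/kg of 2% Lidocaine solution will then be sprayed". Safety Monitoring Plan (a) then relies on the figure: "Lidocaine spray doses will be calculated (7mg/kg based on ideal body weight) to ensure patient is receiving safe doses".

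**Soak.** Before the spray, Group A has cotton soaked in 2% lidocaine with epinephrine held on the donor site. If more hemostasis is needed "following use of 20cc (1 vial) of this Solution A1", epinephrine alone is used. The soak is not scaled to weight.

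**Other support for safety.** The Background cites one precedent, "A prior study where up to 6.7mg/kg of 2% lidocaine with epinephrine was sprayed on donor" sites, and reports that "systemic lidocaine levels were far below toxic levels at their peak (average level of 1.4, with maximum level at 2.2", with the peak at 30 to 60 minutes. Safety Monitoring Plan (a) adds that levels in the first 15 patients were well under toxic values, that higher doses might control pain better, and that the soak method is already in use at the institution. It does not give the doses those 15 patients received.

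**Recording.** The surgical page of the case report form (Appendix C) has times for soak and spray but no volumes. Appendix A and the closing line of Appendix C plan general medication data without naming the study solutions.

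**Draw times.** Study Design (g) counts 60 minutes and 6 hours from application, without saying whether soak or spray. The Group B text ties the 6-hour draw to treatment. The Table of Events footnote (windows of 30 and 60 minutes either side), Appendix A and the case report form all count from the end of the operation, which is not defined.

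**The concern.** The one calculation presented as keeping doses safe leaves out a lidocaine source that the same protocol permits. A reader can add the two limits, but the safety plan does not do so and gives no support for the sum. The precedent in the Background was a spray. The first 15 patients' levels cannot be tied to a dose, and the argument for higher doses leaves open whether those levels cover the present maximum.

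Measured levels are therefore the main check on the combined dose, which makes their timing and the dose record matter. If the first draw comes late, a low value says less about peak exposure. If the volumes used are not kept, the second safety analysis can set a level only against the maximum permitted dose, not the dose the patient received.

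**Working it through.** The 7 mg/kg is a stated limit, not a derived figure, so there is nothing to reproduce. The check is to add up what the text permits.

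**Inputs.** Soak: at most 20 mL (Study Design e) at 2%, which is 20 mg/mL. Spray: at most 7 mg/kg of dosing weight w (Study Design d, e). The documents give no patient weights; 50, 70 and 100 kg are assumed.

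**Permitted applied total.** Total mg = 20 × (mL of soak) + 7w. Full soak = 20 × 20 = 400 mg.

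| Dosing weight | Spray maximum (7w) | No soak | 10 mL soak | 20 mL soak |
|---|---|---|---|---|
| 50 kg | 350 mg | 7.0 mg/kg | 550 mg, 11.0 mg/kg | 750 mg, 15.0 mg/kg |
| 70 kg | 490 mg | 7.0 mg/kg | 690 mg, 9.9 mg/kg | 890 mg, 12.7 mg/kg |
| 100 kg | 700 mg | 7.0 mg/kg | 900 mg, 9.0 mg/kg | 1100 mg, 11.0 mg/kg |

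With a full vial the total is 11.0/7 = 1.6 to 15.0/7 = 2.1 times the figure in the safety sentence.

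On actual weight the total is lower for patients with BMI above 25. A patient of 100 kg and 1.70 m is dosed on 25 × 1.70² = 72.25 kg. The total is 400 + 7 × 72.25 = 906 mg, which is 12.5 mg/kg of dosing weight and 9.1 mg/kg of actual weight.

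**Why the wording needs settling.** The opening words of the Study Design (d) sentence leave slight room for a limit on soak plus spray. After a full soak the two readings give very different maximum spray volumes:

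| Dosing weight | Limit on spray only: 7w/20 | Limit on soak plus spray: (7w − 400)/20 |
|---|---|---|
| 50 kg | 17.5 mL | none (the soak is already 50 mg over) |
| 70 kg | 24.5 mL | 4.5 mL |
| 100 kg | 35.0 mL | 15.0 mL |

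The same sentence says the spray is given in addition, and the other three places attach 7 mg/kg to the spray. Spray-only is the better reading.

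**Draw time.** Let g be the minutes from spray to the start of the post-operative clock (assumed; the documents do not give it). The first draw, 60 minutes with 30 either side, falls g + 30 to g + 90 minutes after the spray.

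| g | First draw, minutes after spray |
|---|---|
| 0 | 30-90 |
| 15 | 45-105 |
| 30 | 60-120 |
| 60 | 90-150 |

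From g = 30 upward, the whole window lies at or beyond the end of the cited 30-60 minute peak. The soak is earlier than the spray, so time since soak is longer still. Study Design (g) gives no window; the 30 minutes is taken from the Table of Events.

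**The case against.** **Each source is capped.** The soak stops at one vial and the spray at 7 mg/kg, so the total is bounded and can be worked out. The safety sentence names the spray and claims no more. This stands: what is missing is a stated and justified total, not a limit. A reader might infer that lidocaine exposure is uncapped; the documents do not support that.

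**Applied is not absorbed.** Some of the soak stays in the cotton, so a millilitre of soak is not a millilitre of spray. The precedent used lidocaine with epinephrine, whereas the Group A spray is lidocaine in saline, and the precedent's weight basis is not given. This stands, and it is why no ratio to 6.7 mg/kg is offered as a measure of risk. A reader might infer that toxic levels are likely. The documents do not show it. Even crude linear scaling, treating soak as spray and assuming the cited levels are in mg/L, gives at most 2.2 × 15.0/6.7 = 4.9, below the Background's seizure figure of more than 5 mg/L. That is close at the extreme, but the scaling is too rough to argue either way.

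**Provisions already exist.** Levels are drawn twice and reflect both sources. Study Design (g) analyses them by patient and by graft area. A second safety analysis follows 10 more evaluable patients. Dispensing records, the fixed vial and recorded height and weight allow each patient's maximum dose to be derived. This stands in part: the amount actually used remains unknown, and no analysis by dose is planned.

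**The clock is only wording.** Spray and draw times are recorded, so elapsed time can be recovered. True for the analysis, but a peak missed because staff followed the post-operative schedule cannot be recovered. A reader might infer that the first draw will miss the peak. The text shows only that it may: the gap is not given, and a 30-60 minute peak seen with epinephrine may not carry over exactly to a plain lidocaine spray.

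**Conclusion.** The point holds and should be corrected. The calculation put forward as securing safe doses omits up to 400 mg of permitted lidocaine. With a full vial the permitted applied total is about 11 to 15 mg/kg at dosing weights of 100 down to 50 kg, and 7 mg/kg if no soak is used. These figures rest on the assumed weights, on reading 7 mg/kg as a spray limit, and on counting the whole vial as applied. They are an upper bound on applied dose and are not evidence of harm.

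The draw clock is inconsistent, and the version on the working forms can place the first draw after the cited peak if the clock starts 30 minutes or more after the spray. That gap is an assumption, so the clock adds little weight of its own. It matters because the levels are the check on a total that the plan does not state.

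**What to change.** 1. Rewrite the sentence in Safety Monitoring Plan (a) to give the maximum soak plus spray dose and its justification, and say whether the first 15 patients' levels were obtained at that dose. Make Study Design (d) and (e), Study Intervention (i) and Safety Monitoring Plan (a) agree that 7 mg/kg is a ceiling on the spray, if that is what is meant.
2. Add mL of study soak used and mL sprayed to the surgical page of the case report form, in both arms so that blinding is kept. That page is completed once per donor site, so volumes need summing per patient.
3. Time both draws from the recorded spray time in Study Design (g), the Table of Events, Appendix A and the case report form, with the windows already stated.
4. Say in Safety Monitoring Plan (f) that the second safety analysis will report levels by actual minutes since soak and since spray, and by total mg/kg applied.

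**Cost.** Wording changes, two form fields and elapsed times derived from times already recorded; no extra draws or patients. The first draw may sometimes fall in the operating room. Recorded volume will still be applied, not absorbed, dose.

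A combined limit on soak plus spray is the sponsor's choice and is not recommended here. It would need a floor at zero and a calculation during surgery, and a smaller spray would reduce the contrast between arms.

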- c. All patients enrolled in the study will have risks and benefits thoroughly explained to them.
- d. Any adverse events will be well documented and thoroughly investigated. Seriousness of event will be assessed by the Principal Investigator. All events deemed serious will be submitted to the University of Florida Institutional Review Board in accordance with institutional policy.
- e. Dressing site will be evaluated daily per standard of care by the burn team until hospital discharge.
- f. After 10 additional evaluable patients, have been enrolled a second safety analysis will be performed; all investigators will be involved in data interpretation.

Analysis Plan

An independent groups t-test (Student's t-test) will be performed to compare the mean rating between the difference of the two reported pain scale ratings. Each patient will be used as his/her own control by comparing the amount of narcotics utilized prior to surgery. An alpha level of 0.05 and power of 0.8 will be used to address the difference in the two groups. Given the desired alpha the sample size was estimated by pre-determined tables for certain values, by Mead's resource equation. With an effect size (Cohen's d) of 0.8 it is estimated that 25 patients in each

group will be needed in order to show statistical significance. An interim analysis will be conducted at 10 patients in each group and significance will be analyzed.

The amount of hydromorphone utilized in the PACU immediately post op and within the first 24 hours will be compared between the two groups and trended within the same group. Once again, an independent groups t-test will be performed to compare the mean quantity of hydromorphone required between the two groups. An alpha level of 0.05 and power of 0.8 will be used to address the difference in the two groups.

7. Possible Discomforts and Risks:

The patient's regular medical care will not change because they are enrolled in this study.

Possible risks to you may include:

- The risks from skin grafting and donor site include those associated with any surgical procedure that involves general anesthesia. These include reactions to the anesthesia, medications, nausea, pain, problems breathing, excessive bleeding, and infection.

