Appendix A.

DATA COLLECTION POINTS

Age
Race
Sex
Height
Weight
BMI
Date of Injury/Wound
Mechanism of Injury/Wound
TBSA % Burned /Size of wound
Medical History
Physical Exam
Randomization
OR Procedure
OR Date
OR Incision Time
OR Extubation Time
OR Medication Data Collection
Donor Site Dimensions
Lidocaine levels at 60 minutes and 6 hours post op
Time of Study Treatment Soak Placement
Additional Epinephrine Soak Required
Time of Study Treatment Spray Placement
Time of Therabond Placement

Time of PACU/BICU Admission (Post-operatively)

PACU/BICU Post –op Narcotic Medication

Documentation of Verbal Numerical Rating Scale Pain Assessment (Time): 30 minutes after extubation, 2 hours, 6 hours and 24 hours post op obtained by research staff for both donor site and overall pain

Self- Reported Pain Assessment (Time): Collect from EPIC for first 24 hours

Wound Healing Assessment (14-21 days post op[+/-5days]) Performed per standard of care

Photographs (OR and 14-21 days post op[+/-5days])

Adverse/SA Event Assessment

Overall Narcotic Medication Data Collection from EPIC (0-72 hours post op)

[figure not shown]
Date of new onset infection of donor site

Antibiotics for donor site infection

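### The pain t-test ignores donor-site area, which is fixed before treatment and already collected; naming it as a covariate is a low-cost precision gain of unknown size

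*Combined protocol and SAP*

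**What the plan says.** The Analysis Plan (section 6) tests pain with "An independent groups t-test" (Student's), used to "compare the mean rating between the difference of the two reported pain scale ratings". It does not say which two ratings are meant, and it names no covariate. On error rates it says "An alpha level of 0.05 and power of 0.8 will be used to address the difference in the two groups". On size it says "With an effect size (Cohen's d) of 0.8 it is estimated that 25 patients in each" group, and Study Design item e gives the total as "50 patients split into two (study & control) groups". Sidedness is not stated.

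Study Design item b admits burn and wound patients having a "split thickness skin graft with a 1-15% TBSA donor site". The randomization paragraph under Study Procedures describes computer-generated numbers and no stratification.

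Appendix A lists "Donor Site Dimensions" among the data to collect. The Surgical Procedure form in Appendix C records them in cm and cm², one page per donor site. Study Design item e places the soak after harvest. Items f and g relate narcotic use to donor-site area and lidocaine levels to graft area. Nothing comparable is planned for the pain scores. Burn or non-burn mechanism is on the Baseline form.

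**The concern.** Pain after harvest could plausibly depend on how much skin was taken, and eligibility permits a 15-fold range. A covariate that predicts the outcome and that treatment cannot affect lowers the residual variance when it is put in the model, and so narrows the confidence interval at the same number of patients. Donor-site area meets the second condition: it is settled before the soak is applied. The plan itself treats area as relevant to two other outcomes.

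The stake is modest but falls on the comparison that sized the trial. By the exact t calculation that comparison has slightly under 80% power, and no dropout allowance is stated. With 25 per arm, the difference between arms in the mean of any covariate has a standard error of sqrt(2/25) = 0.28 SD, so a chance imbalance above 0.3 SD arises in about 29% of trials. The choice of covariate is credible only if it is made before the data are compared by arm.

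**Working it through.** **Inputs from the documents.** d = 0.8, alpha 0.05, power 0.80, 25 per arm (Analysis Plan). Two-sided testing is assumed, because it reproduces 25; one-sided testing gives 20.

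**The plan's own figure.** Normal approximation: n = 2(1.960 + 0.842)²/0.8² = 24.5, so 25 per arm, as stated. Exact check: noncentrality 0.8 × sqrt(25/2) = 2.828 on 48 df gives power 0.791; 26 per arm gives 0.807. The stated size reproduces to within one patient per arm.

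**Input the documents do not give.** R², the share of within-arm variance in the pain outcome explained by the covariates. Assumed range: 0 to 0.30.

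**Formula with adjustment.** For k covariates and N = 50, the variance of the treatment difference relative to the t-test is

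V = (1 − R²) × [1 + k/(N − 3 − k)].

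The bracket is the average cost of chance covariate imbalance: 1 + 1/46 for area alone, 1 + 2/45 for area plus burn versus non-burn. Power comes from the noncentral t with effect 0.8/sqrt(V), on 47 or 46 df. The confidence interval width changes by the factor sqrt(V), ignoring a negligible change in the t quantile.

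Example, area alone, R² = 0.10: V = 0.90 × 1.0217 = 0.920; sqrt(V) = 0.959; effect 0.8/0.959 = 0.834; power 0.82.

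| Assumed R² | Power, area alone | CI width, area alone | Power, both covariates |
|---|---|---|---|
| 0 | 0.78 | +1% | 0.77 |
| 0.05 | 0.80 | −1% | 0.79 |
| 0.10 | 0.82 | −4% | 0.81 |
| 0.20 | 0.87 | −10% | 0.86 |
| 0.30 | 0.91 | −15% | 0.90 |

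The unadjusted comparator is 0.79 in every row.

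**Break-even.** Adjusted power equals 0.791 at R² of about 0.02 with area alone (a correlation of about 0.15), and at about 0.04 with both covariates. Below these values adjustment costs a little.

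**Simulation check.** 20,000 trials per setting were simulated, with size uniform on 1–15% TBSA and one covariate. At correlations of 0, 0.3, 0.5 and 0.6, adjusted power was 78.5%, 82.2%, 88.6% and 93.2%; the formula gives 78.2%, 81.9%, 88.6% and 92.9%. Type I error was about 5% for both methods.

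**The case against.** An unadjusted t-test in a randomised trial is valid, and chance imbalance in donor size is random error that its standard error already covers. Both statements stand. A reader might infer that the planned pain result would be biased or the trial undersized. The documents support neither: type I error is about 5% with or without adjustment, and the stated 25 per arm reproduces.

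A reader might also infer that power is certainly being given away at no cost. That is not supported either. The 1–15% TBSA figure is an eligibility limit, not an observed spread, and a wide permitted range does not show that size predicts pain. Two features of the protocol could weaken the association. Post-operative analgesia is escalated according to pain (Study Design item c), so a larger donor site may show up in opioid use more than in VNRS. And if the outcome is a within-patient difference of two ratings, part of any size effect may cancel. Adjustment also has a small price when R² is near zero.

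Finally, the Surgical Procedure form gives no time for the measurement. The documents show that the area is determined before study treatment, not that it is written down before it.

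These points limit the size of the claim. They do not remove it: the covariate is legitimate, collected, and already used elsewhere in the plan.

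**Conclusion.** The point holds as an optional, low-cost improvement to precision, not as an error. With area alone, the adjusted analysis would gain about 3 points of power at R² = 0.10 and about 11 points at R² = 0.30, and would lose about 1 point if area explains nothing. With burn versus non-burn added, the worst case is a loss of about 2 points. All these figures rest on d = 0.8, 25 evaluable patients per arm, two-sided testing at 0.05 and an assumed R². Where the trial lies in that range cannot be read from the documents. The point concerns the pain comparison only.

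**What to change.** First name one pain outcome and one time point, for example donor-site VNRS at a stated scheduled assessment. The current wording does not identify which ratings are compared, and there are four scheduled times and two ratings (donor site and overall).

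Then pre-specify, before unblinding and before any further comparison by arm, a linear model of that outcome on arm and log total donor-site area in cm². Sum the area over the per-site Surgical Procedure pages. Burn versus non-burn may be added; it is optional and roughly doubles the worst-case cost. Report the adjusted mean difference with its 95% CI, and keep the unadjusted t-test as a sensitivity analysis.

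The cost is a few sentences in the Analysis Plan. No new data, visits or patients are needed. It would also help to state on the form that dimensions are measured before the soak.
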